2.1.3 Mitigating Bias

Subjects will be randomly assigned to a treatment sequence (see section 3.1.2). Identities of the study investigational products will be disguised with a study label. Similar sized kit boxes will be used to ensure product blinding. All treatment products will be dispensed in a secluded area, away from the study examiner, to maintain the study blind. All subjects will receive the same product for Period 5.

The treatment product(s) each subject will receive will not be disclosed to the Principal Investigator, examiners, study center personnel, subjects, contract monitors, contract vendors, or the Sponsor, except for select site personnel responsible for usage instruction and supervised use. Period 5 product will be blinded to analytical personnel.

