2.1.2 Design Type

This is a randomized, four-treatment, 4-period crossover, double blind clinical trial. The target population is approximately 16 adult volunteers. During the course of the study, all subjects will be asked to voluntarily participate in a fifth period, not included as part of the crossover design. Those subjects willing to participate in Period 5 will sign an amended informed consent form and will all receive the same product during that period. Two to three days before the start of each treatment period the subjects will have their teeth cleaned to remove all accessible plaque and calculus and will be provided with a non-fluoride dentifrice to use until their next visit. At the beginning of each testing period, two gauze-covered 4 mm round partially demineralized human enamel specimens will be placed in the buccal flange area of the subject's mandibular partial denture. In addition, two gauze-covered 4 mm round partially demineralized human enamel specimens will be placed in the buccal surface of two posterior denture teeth of the same side of the partial denture. Once specimens are placed, subjects will wear their partial dentures twenty-four hours a day and use their assigned toothpaste twice daily, as instructed, until their next visit. Subjects will return at 7 and 14 days to have one specimen removed per visit, and again at 21 days to have the remaining two specimens removed. The specimen removal sequence will occur in a predetermined order starting with the anterior denture tooth specimen, posterior denture tooth specimen, and then the two buccal flange specimens. Following the 21-day specimen removal visit, the subjects will undergo a four- to five-day washout period followed by another cleaning and two- to three-day lead in period. This process will be repeated until all subjects have used all four test products. Changes in the mineral content of the enamel specimens will be assessed using the SMH. Enamel fluoride uptake (EFU) will be determined using the microdrill enamel biopsy technique.

Table 1. Study Schedule by Procedure Type and Visit

PROCEDURE	VISIT 1	VISIT 2, 7, 12, 17, 22	VISIT 3, 8, 13, 18, 23	VISIT 4, 9, 14, 19, 24	VISIT 5, 10, 15, 20, 25	VISIT 6, 11, 16, 21, 26
	SCREENING	PROPHY	BEGIN TREATMENT	7 DAY REMOVAL	14 DAY REMOVAL	END ¹ TREATMENT
Informed Consent	X					
Medical History Review	X	X	X	X	X	X
Demographics	X					
Oral Soft Tissue Exam	X	X	X			X
Oral Hard Tissue Exam	X	X (v2 only)				X (v21 and v26)

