Each subject will receive an OST examination, answer continuation questions and have their medical history/medication information updated. Subjects will be asked to return the washout product they received at Visit 2 and will be given their randomized study product and diary for product use. Subjects will be instructed on the brushing method (see Appendix). The four enamel partially demineralized specimens will be placed in the buccal flange/posterior teeth areas on one side of the subject's mandibular partial denture. All subjects will be instructed to wear their partial denture containing the enamel specimens 24 hours a day except during the cleaning of their natural teeth (twice per day) and for short periods to rinse their mouth out with tap water after meals and snacks.

Visit 4 (7 Day Removal)

Seven (7) days following Visit 3, the subjects will return to the Institute and answer continuance criteria questions and update their medical history/medication information. One enamel specimen will be removed from anterior denture tooth site of their partial denture and the hollow will be filled with a temporary dental material (DentuSil™). The subjects will be told to continue using their assigned product as instructed.

Visit 5 (14 Day Removal)

Fourteen (14) days following Visit 3, the subjects will return to the Institute and answer continuance criteria questions and update their medical history/medication information. One enamel specimen will be removed from posterior denture tooth site of their partial denture and the hollow will be filled with a temporary dental material (DentuSil™). The subjects will be told to continue using their assigned product as instructed.

Visit 6 (End Treatment Period 1)

Twenty-one (21) days following Visit 3, the subjects will return to the Institute and receive an OST examination, answer continuance criteria questions and update their medical history/medication information. Subjects will be asked to return the study product and diary they received at Visit 3. The remaining two enamel specimens in the buccal flange site will be removed from their partial denture and the hollows will be filled with a temporary dental material (DentuSil)

Period 2, 3, 4 & 5

The procedures outlined above (Visit 2-6) will be repeated until each subject has used each of the four test products, followed by a 5th test product in Period 5. At Visit 21 (and also at Visit 26 for those subjects

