3. TREATMENTS

3.1.1 Product Usage

Washout Product:

Subjects will be instructed to brush twice daily (morning and at bedtime) with their washout toothpaste and toothbrush following the brushing instructions found in the Appendix.

Treatment Product:

Subjects will be instructed to brush twice daily (morning and at bedtime) with their assigned dentifrice for 21 days following the brushing instructions found in the Appendix. Subjects will be instructed to brush the biting surfaces of their back teeth (but not enamel specimens) with a full ribbon of study dentifrice for one timed minute while wearing their partial dentures, followed by rinsing with the 15 mL of measured tap water for 10 seconds and then expectorating. Subjects who are regular floss users will be allowed

to continue flossing; use of any non-study related products will be disallowed. Compliance with brushing procedures will be recorded in subject diaries (see Appendix), as well as any *de novo* or changes in medical conditions, medications or treatments.

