3.2 Assessment of Efficacy

3.2.1 Sample Collection

Salivary Flow Assessment

Salivary flow will be assessed during the screening visit. For the unstimulated collection, subjects will sit quietly for five minutes before beginning the test. During the five-minute test time, they will be told to allow their saliva to pool, emptying into a collection cup whenever they feel the need to swallow.

For the stimulated collections, subjects will chew unflavored gum base for one minute and then swallow any pooled saliva. They will then chew the gum base for two minutes, during which time they will empty any pooled saliva into a collection cup.

The samples will be weighed and the salivary flow rates determined. The unstimulated saliva flow rate must be ≥ 0.2 mL/min and the stimulated saliva flow rate must be ≥ 0.8 mL/min for study qualification.

Diary for Home Use

At the start of each treatment period, subjects will be provided with a diary (see Appendix) to record the date, and the time of the morning (a.m.) and evening (p.m.) of each brushing and any deviation from the brushing regimen. In addition, subjects will also record any new or changes in pre-existing medical conditions, medications or non-drug treatments or any change in signs or symptoms that may occur.

Subjects will be required to bring the completed diary to the end of treatment visit. Study staff will review the Diary with the subject to confirm treatment compliance and clarify listed medical conditions, medications and non-drug treatments.

Intra-oral Appliance

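### Section 2.1.3 lets staff who instruct subjects be told the product in a double-blind crossover, although no task described in the protocol needs that knowledge

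*Combined protocol and SAP*

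**What the plan says.** Section 2.1.2 states the blinding level: "This is a randomized, four-treatment, 4-period crossover, double blind clinical trial". Section 2.1.3 says that product identity "will not be disclosed to the Principal Investigator, examiners, study center personnel, subjects, contract monitors, contract vendors, or the Sponsor", and then makes an exception: "except for select site personnel responsible for usage instruction and supervised use". The exception is not limited to any period. Section 2.1.3 treats Period 5 in separate sentences: everyone receives the same product, and blinding is specified for the analytical personnel.

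Section 3.1.1 has subjects brush "with their assigned dentifrice for 21 days following the brushing instructions found in the Appendix". Section 2.1.5 places the instruction at the visit that opens a treatment period and then says: "The procedures outlined above (Visit 2-6) will be repeated until each subject has used each of the four test products". On compliance, Section 3.2.1 says: "Study staff will review the Diary with the subject to confirm treatment compliance".

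**The concern.** The staff who teach brushing can plausibly affect how much paste is used, how often, and how the rinse is done. If they know which period is 0 ppm and which is 2800 ppm, their instruction, their follow-up questions and their handling of discrepancies can differ by product without anyone intending it. The primary comparison is enamel fluoride uptake at Day 21 between these two pastes (2.1.1), so the exposure falls on the main contrast.

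An exception of this kind can be justified when products are used differently or when someone must watch them being used. The question is whether this protocol contains such a need, and whether it keeps the excepted staff away from tasks where knowledge could matter.

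**Working it through.** The plan states no figure that could be reproduced here, and no formula decides the point. The check is to compare the sections.

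1. **Does instruction differ by product?** No. Sections 1.5 and 3.1.1 and the Appendix give one regimen for all test products: the same ribbon of paste, timed minute, measured rinse and diary entries. Section 2.1.5 repeats the same visit procedures in each period. The kit already contains the use instructions (2.1.4).

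2. **Is any use supervised?** None is described. Table 1 has no row for it. The visit descriptions in 2.1.5 do not mention it. Section 3.1.4 checks use by weighing returned tubes and comparing the result with the diary. The Appendix describes brushing at home. Supervised brushing is otherwise mentioned only in the background (1.1), which describes published trials.

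3. **Does dispensing need the identity?** Not in Periods 1-4. Labels disguise the products (2.1.3), kits carry letter codes (2.1.4), and the sequences in 3.1.2 are written in the letters A to D.

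4. **How else may the identity be learned?** Sections 2.1.4 and 2.1.8 describe one route, a sealed report with scratch-off cover. It is opened for a serious adverse event or where management of a subject depends on knowing the product, with the date, time and reason recorded. The exception in 2.1.3 permits disclosure with no stated reason, no log and no named role.

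5. **Are the excepted staff kept away from sensitive tasks?** Section 2.1.3 separates dispensing from the examiner but sets no such rule for instructing staff. Diary review is assigned only to study staff (3.2.1). Discussion of usage discrepancies is as needed, with no role named (3.1.4). The continuance questions can lead to exclusion from the study or the analysis (2.2.3), and who asks them is not stated.

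6. **Scope.** 16 subjects x 4 crossover periods = 64 planned subject-periods fall under the exception. This counts where the wording applies. It does not measure bias.

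7. **Period 5.** Its kits are not letter-coded (2.1.4) and it is left out of the code breaker arrangement (2.1.4, 2.1.8). An edit for Periods 1-4 should not be carried over to it unchanged.

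**The case against.** The strongest reply is that the exception has no practical effect. No section hands these staff the identity in Periods 1-4, and the labels, letter codes and sealed report all point the other way. The sentence may be leftover wording. That cannot be confirmed, but it is a fair reading, and it bars the stronger inference a reader might draw, that instructing staff do know the product. The documents show that disclosure is permitted, not that it happens. The reply does not save the sentence. If it is leftover it conflicts with the rest of the scheme, and if it is operative it weakens the blind without a reason.

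The second reply is that the safeguards that matter most remain. Subjects, the principal investigator, examiners, monitors, vendors and the sponsor are listed as blinded, and the primary endpoint is a fluoride-electrode measurement (4.4.2). This stands. It limits measurement bias, but it leaves instruction and compliance counselling open.

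A reader might also infer that the per-protocol set would shift. The documents do not support that. Section 3.1.4 fixes non-compliance at 15% or more of treatments missed, cross-checks use by tube weight, and requires only that the reason be noted. Section 5.4.2 defines the per-protocol set by major protocol deviations and does not refer to that threshold. Where 2.1.6 and 2.2.3 call for a judgment on deviations, it belongs to the investigator, who is listed as blinded.

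Finally, a reader might turn missed brushings into a percentage change in uptake. That needs an assumed change in adherence and an assumed proportional response, and the documents give neither. Under proportionality, extra brushing would rescale a real product effect and could not create one where none exists.

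**Conclusion.** The point holds as a defect in the blinding rule. The exception serves no task described in the protocol. As written it is inconsistent with the double-blind design and with the restricted code-break route. It also leaves instruction, diary review and discrepancy discussions open to staff who may know the product. Its scope is all 64 planned crossover subject-periods. The size of any bias cannot be estimated, and no claim is made that results would move by a given amount or that the trial is invalid.

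The conclusion rests on reading the exception plainly, as permission to disclose, and on the protocol describing all product-related tasks. That instructing staff can influence brushing is a reasonable inference, not something the documents state. Because both the leftover and the operative readings call for an edit, the sponsor should make it.

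**What to change.** For Periods 1-4, delete the exception from 2.1.3, including its reference to supervised use. All site staff with subject contact are then blinded, and identity is available at the site only through the sealed code breaker under the existing rules in 2.1.4 and 2.1.8.

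Add a separate statement for Period 5: all subjects receive the same product, and only the analytical personnel are blinded. Without it, deleting the exception would make 2.1.3 appear to promise a site-level blind in Period 5 that the labelling does not provide.

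If the sponsor has a need that the protocol does not state, keep a narrow exception instead. Name the roles, give the reason, describe any supervised use, and bar those staff from diary review, compliance discussions and continuance questions.

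Deletion changes one sentence, and the Period 5 statement adds another. On the procedures described there is essentially no operational cost, because instructions are the same for every product and the Periods 1-4 kits are already coded. The narrow exception would cost some separation of site duties.

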2.1.4 Labeling and Shipping

The identity of the toothpaste will be disguised. Subjects will receive a kit box containing 1 tube of toothpaste, a timer, a toothbrush and product use instructions to be used throughout the duration of their study period. Subjects will receive a new kit box at the beginning of each study period.

The kit boxes will be labeled by letter code (except Period 5). Kit box labels will also contain the study number, emergency phone number, distributor name/address, appropriate caution statements, content statement and other information as required by internal regulations and clinical SOPs. The shipping containers will be labeled with the clinical site address and a content statement listing study number and kit box numbers contained within. Supplemental products will be provided to site.

The site will be provided with a code breaker report in a sealed envelope. The sealed code breaker report contains documents that list the kit box number or treatment code while the identity of the treatment products is hidden by an opaque scratch-off seal (except Period 5). If the study blind needs to be broken, an individual subject's investigational product may be ascertained by opening the sealed code breaker report, locating the subject's kit box number or treatment code and scratching off the opaque seal to reveal the treatment identity. The sealed code breaker report will be opened if a clinically serious AE occurs or management of the subject requires knowledge of the identity of the investigational product. The Investigator should immediately inform the Sponsor that the code will be broken and record the date, time and reason for breaking the code in writing. After the study is complete and the study database has been finalized and locked, the site will return the code breaker report to the Sponsor using the self-addressed, stamped envelope provided by the Sponsor.

2.1.5 Duration of Subject Participation

Visit 1 (Screening)

Subjects who have been recruited for the study via a telephone interview will sign in at the study site for this and all subsequent visits. At this time, subjects will be asked to read and sign duplicate copies of an informed consent statement, authorization for the release of health information for research form and demographic form. Demographic information and study entry criteria will be obtained and documented on the appropriate case report form (CRF). Upon review of these documents, an update of their medical

history/medications and the inclusion/exclusion criteria, each subject will be given an oral soft/hard tissue exam (OSHT) prior to their acceptance into the study. Their mandibular partial denture will be examined to determine if specimens can be held in one buccal flange area and the posterior denture teeth of the same side, as previously described. They will then provide a stimulated and unstimulated saliva sample to determine salivary flow rate. If no contraindications to their participation are discovered and the subject meets the study requirements, the subject will be accepted into the study.

General comments, if any, will be recorded on the appropriate CRF.

Visit 2 (Prophy Period 1)

Two to three days prior to the beginning of Treatment Period 1, subjects will return for a professional dental prophylaxis. Subjects will answer have their medical history/medication information updated and answer continuation questions. Subjects will then receive an oral soft tissue exam (OST) and oral hard tissue exam (at the first period only). The subject's mandibular partial denture will be prepared to hold the round enamel specimens by drilling out hollows in the partial dentures at the specimen sites in the buccal flange area and the buccal surface of two denture teeth on the same side of the partial denture. A temporary dental material (DentuSil™) will be placed in the drilled-out areas of the partial denture. Subjects will be given fluoride-free toothpaste to use at home for the next two to three days until they return for their next visit. They will be encouraged to remove their partial denture at night until their next visit.

Visit 3 (Begin Treatment Period 1)

Each subject will receive an OST examination, answer continuation questions and have their medical history/medication information updated. Subjects will be asked to return the washout product they received at Visit 2 and will be given their randomized study product and diary for product use. Subjects will be instructed on the brushing method (see Appendix). The four enamel partially demineralized specimens will be placed in the buccal flange/posterior teeth areas on one side of the subject's mandibular partial denture. All subjects will be instructed to wear their partial denture containing the enamel specimens 24 hours a day except during the cleaning of their natural teeth (twice per day) and for short periods to rinse their mouth out with tap water after meals and snacks.

Visit 4 (7 Day Removal)

Seven (7) days following Visit 3, the subjects will return to the Institute and answer continuance criteria questions and update their medical history/medication information. One enamel specimen will be removed from anterior denture tooth site of their partial denture and the hollow will be filled with a temporary dental material (DentuSil™). The subjects will be told to continue using their assigned product as instructed.

Visit 5 (14 Day Removal)

Fourteen (14) days following Visit 3, the subjects will return to the Institute and answer continuance criteria questions and update their medical history/medication information. One enamel specimen will be removed from posterior denture tooth site of their partial denture and the hollow will be filled with a temporary dental material (DentuSil™). The subjects will be told to continue using their assigned product as instructed.

Visit 6 (End Treatment Period 1)

Twenty-one (21) days following Visit 3, the subjects will return to the Institute and receive an OST examination, answer continuance criteria questions and update their medical history/medication information. Subjects will be asked to return the study product and diary they received at Visit 3. The remaining two enamel specimens in the buccal flange site will be removed from their partial denture and the hollows will be filled with a temporary dental material (DentuSil)

Period 2, 3, 4 & 5

The procedures outlined above (Visit 2-6) will be repeated until each subject has used each of the four test products, followed by a 5th test product in Period 5. At Visit 21 (and also at Visit 26 for those subjects

participating in Period 5), subjects will receive an OSHT examination, have their mandibular partial denture cleaned through sonication, if applicable, have their partial denture repaired (if not going on to another in situ study) and their participation in the study will end.

Subject Accountability

If, for any reason, a subject does not complete the study, an explanation will be entered on the Subject Accountability CRF. All data gathered on the subject prior to discontinuation will be made available to the Sponsor.

General Comments and Adverse Events

General comments can be recorded at any time during the study. Adverse Events (AEs) will be documented on the AE CRF. Any self-reported AE that remains unresolved by the end of the study should be followed up until resolution by the investigator/designee, and the resolution should be documented only as source documentation. If a subject is unreachable to determine whether the AE has been resolved, the attempts to contact the subject should be documented as source documentation. Examiner observed AEs that are unresolved at the end of the study are followed to resolution at the discretion of the Medical Monitor.

